1.1. Study Objectives

Specific Aims

1. Determine the effect of progressive nicotine content reduction on nicotine and its metabolites and other biomarkers of smoking exposure.
 - a. Determine the effects of RNC (reduced nicotine content) cigarettes in both black and white smokers of lower SES (socioeconomic status) over an 18 week trial period. Subjects will be randomized to either, (i) gradual reduction in reduced nicotine content cigarettes, or (ii) cigarettes containing the nicotine content of their usual brand. It is expected that the gradual reduction of nicotine from progressively lowering nicotine exposure will lead to lower levels of blood nicotine metabolites and nicotine-derived 4-(methylnitrosamino)-1-(3-pyridyl)-1-butanol)(NNAL), while not affecting cigarettes smoked per.
 - b. Determine the modifying effect of menthol on progressive nicotine content reduction and biomarkers. It is expected that menthol will not modify the effect of progressive RNC cigarettes on the above biomarkers.
2. Determine the predictors of participant drop-out/relapse. We hypothesize that compensatory smoking behavior as measured by smoking topography and expired carbon monoxide (CO), a higher baseline nicotine dependence behavioral score, will be associated with dropout/ relapse.
3. Determine if a gradual reduction in RNC cigarettes vs. same nicotine content is associated with a reduction in stress. Psychological stress and nicotine stimulate the production of cortisol, a biomarker of stress pathways. It is expected that nicotine reduction will lead to initially higher levels

of psychological stress and cortisol associated with withdrawal but lowered levels of psychological stress/cortisol with long-term nicotine reduction.

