9.1. Sample size determination

The primary sample size calculation for this project will be based on hypothesis 1a and the main outcome variable is plasma cotinine concentration (measured as ng/ml). The mean value of this continuous variable will be compared between the control group and the experimental group. For plausible effect size and variation, we use results of Benowitz et al [4], where the mean (SD) of plasma cotinine concentration are 240 (120) for the control group and 113 (116) for the experimental group at the 21st week follow-up visit (end of randomization phase for trial). It is expected that the cotinine level in the experimental group is reduced gradually after the randomization and the mean difference of the cotinine level between these two groups at the beginning of the trial for our study will be smaller than the value of 127 ng/ml in Benowitz et al [4]. With a sample size of 70 participants per group, we are able to detect the difference in plasma cotinine concentration level between the two groups as small as 58 ng/ml with at least 80% power (and 68 ng/ml with at least 90% power). In this project we plan to study the mean change of plasma cotinine concentration separately for black and white populations. A total sample size of 280 (70 per group * 2 groups * 2 races) is then needed for this project. We plan to recruit a total of 400 participants for this project by allowing a 30% drop-out rate. The alpha level used for the power analysis is 0.05. Another biomarker of interest is the Glutathione (GSH, measured in μ mol/ml). Within each study population (black or white), a sample size of 70 per

group will enable us to detect a mean difference of GSH of 0.23 with at least 90% power. The common standard deviation is assumed to be 0.40 based on [name] et al (2004). For testing the menthol-by-group interaction effects, our proposed sample size will give us at least 80% power to detect a mean difference of plasma cotinine concentration of 72 ng/ml in the pair-wise comparison of among the group-by-menthol combination (4 levels, alpha is adjusted to 0.0083 by Bonferroni method).

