To determine the modifying effect of menthol on progressive nicotine content reduction and biomarkers: modification effects such as the menthol will be examined by incorporating the menthol-by-group interaction in the multi-variable linear mixed model. The three-way interaction of the menthol-by-group-by-time will be explored but will be removed from the model if not significant. If the menthol-by-group interaction were found significant then mean-profile plot will be used to show the interaction in details.

To determine the predictors of participant drop-out/relapse: it is hypothesized that compensatory smoking behavior as measured by smoking topography and expired carbon monoxide, a higher baseline nicotine dependence behavioral score and rapid nicotine metabolism phenotypes will be associated with drop-out/relapse. The status of drop-out/relapse will be combined with the length of time from randomization to drop-out/relapse or loss of follow-up to form a time-to-event type of variable. Participants who completed the randomization phase of study will be considered as censored records. Kaplan-Meier type analysis (for categorical predictors) or simple Cox proportional hazard regression model (for quantitative predictors) will be used to examine the bivariate associations between the possible predictors and time to drop-out. If a predictor has shown marginal significance (with p-value less than 0.10) in the bivariate analysis then it will be kept in the multiple regression analysis. A multi-variable Cox proportional hazard regression

model will be built to examine the effects of the predictors jointly for time to drop-out. The magnitude and direction of effectiveness will be quantified by the estimated hazard ratios with their 95% confidence intervals. The interaction between the predictors will be explored in the analysis but will be removed if not significant.

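### The Aim 2 predictors are hypothesised in advance, yet each must pass a bivariate p<0.10 screen to get an adjusted hazard ratio, and weak effects that pass tend to be overstated

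*Combined protocol and SAP*

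**What the plan says.** Section 1.1 (Aim 2) states a directional hypothesis about "compensatory smoking behavior as measured by smoking topography and expired carbon monoxide (CO), a higher baseline nicotine dependence behavioral score". Section 9.2 repeats it and extends the list: "a higher baseline nicotine dependence behavioral score and rapid nicotine metabolism phenotypes will be associated with drop-out/relapse". Together the two sections name four constructs.

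Section 9.2 then sets out the analysis. Each possible predictor is first examined alone, by a Kaplan-Meier type analysis or a simple Cox model. One with "marginal significance (with p-value less than 0.10) in the bivariate analysis then it will be kept in the multiple regression analysis". After that a multivariable Cox "model will be built to examine the effects of the predictors jointly for time to drop-out", and results are given as "estimated hazard ratios with their 95% confidence intervals". On follow-up: "Participants who completed the randomization phase of study will be considered as censored records".

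The screen applies to any predictor and does not exempt the hypothesised ones. No shrinkage, bootstrap or other allowance for selection is described. Section 9.2 forces known confounders into the linear models but has no matching sentence for the Cox model, so nothing is guaranteed entry there, not even study arm.

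**The concern.** A p-value screen belongs to an open search among many candidates. Aim 2 is a short list written down in advance, and its joint model exists to show how those predictors act together. Screening first has two effects:

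- **Lost estimates.** A hypothesised predictor that misses p<0.10 on its own never gets an adjusted hazard ratio. That includes one whose effect shows only after adjustment for another.
- **Overstated estimates.** When power is low, a weak effect passes mainly in trials where chance made it look larger. The hazard ratio and interval are then reported as though no selection had occurred.

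At stake is the description of which smokers leave a reduced-nicotine regimen. Product compliance/drop-out is also the primary endpoint listed in section 1.2.

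**Working it through.** **Inputs from the documents.** Section 9.1: 280 completers and a 30% drop-out rate ("We plan to recruit a total of 400 participants for this project by allowing a 30% drop-out rate"). Section 7.2.1: topography in a random subset of 100. Section 9.2: screen at p<0.10, 95% intervals.

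**The plan's own figure.** 280 / (1 − 0.30) = 400, which agrees.

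**Assumed inputs.**
- Events: 400 × 0.30 = 120 overall and 100 × 0.30 = 30 in the topography subset. Neither count is stated in the documents. The subset is chosen before randomisation, so it may yield fewer; relapse is not defined and could add some.
- Effect sizes: the documents give none for Aim 2, so a range of 1.2 to 1.5 per SD is shown.
- Each predictor enters as one fixed value, and tests are two-sided.

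**Formulas.** For a predictor scaled to SD 1, SE(log HR) = 1/√events and μ = log(HR)/SE. With c = 1.645:
- P(pass) = Φ(μ − c) + Φ(−μ − c)
- E[Z | pass] = μ + [φ(c − μ) − φ(c + μ)] / P(pass)
- HR when kept = exp(SE × E[Z | pass])

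**Worked case: 120 events, HR 1.20.** SE = 1/√120 = 0.0913 and μ = 0.1823/0.0913 = 1.997. P(pass) = Φ(0.352) + Φ(−3.642) = 0.638, so 36% are dropped. E[Z | pass] = 1.997 + (0.3749 − 0.0005)/0.638 = 2.584. HR when kept = exp(0.0913 × 2.584) = 1.27.

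| Events | True HR per SD | Dropped | HR when kept | 95% CI coverage when kept |
|---|---|---|---|---|
| 120 | 1.2 | 36% | 1.27 | 96% |
| 120 | 1.3 | 11% | 1.33 | 97% |
| 120 | 1.5 | 0.3% | 1.50 | 95% |
| 30 | 1.2 | 74% | 1.49 | 89% |
| 30 | 1.3 | 58% | 1.54 | 94% |
| 30 | 1.5 | 28% | 1.64 | 97% |

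**Predictor with no effect.** Among those that pass, the 95% interval excludes 1.0 in 0.05/0.10 = 50%. Over all trials that is still 5%.

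**Check in the multivariable model.** The table screens and reports the same univariate estimate, so the joint model was also simulated (four predictors, 30% events, 2,000 replicates).
- *Independent predictors, true HR 1.30, N = 400.* Kept about 87% of the time, mean HR 1.33 when kept. Unscreened: 1.30 to 1.31, coverage 95% to 96%.
- *Independent predictors, true HR 1.30, N = 100.* Kept about 40%, mean HR about 1.55 when kept. Unscreened: about 1.32, coverage about 94% to 95%.
- *Correlation 0.3, all effects in the same direction, HR 1.30.* N = 400: almost never dropped, and no inflation. N = 100: kept about 80%, mean HR about 1.39 to 1.40.
- *Correlation 0.3, one effect of opposite sign (true HR 0.77), N = 400.* That predictor is dropped 71% of the time; when kept it averages 0.70 with 89% coverage. The unscreened model estimates 0.77. The two positive effects average about 1.28 when kept, against 1.31 unscreened.

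**The case against.** The strongest defence is that Aim 2 is secondary modelling: it has no power calculation, the sample size rests on hypothesis 1a, and a lenient 0.10 screen is common practice. That bears on priority, but it does not make the screen useful for a list of four constructs.

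Several stronger readings are tempting and should be resisted:

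- **That the screen removes a predictor from its own test.** The hypothesis is one of association, and section 9.2 examines that for every possible predictor before any screening. What is lost is the adjusted estimate.
- **That every reported hazard ratio is biased away from 1.** At 120 events the inflation is small at HR 1.3 and absent at 1.5. With correlated predictors some retained hazard ratios move towards 1.
- **That the intervals generally lose their level.** At 120 events, coverage given passing is 95% to 97% for HR 1.2 to 1.5. It falls to 89% for HR 1.2 at 30 events. The 50% figure for a null predictor is conditional on passing; the overall false-positive rate is not raised.
- **That one joint model with all named predictors has ample events.** Topography is measured in only 100 participants and comprises several measures (section 1.3.3 lists four; section 7.2.1 also mentions puff velocity and interpuff interval). Four topography measures plus CO, dependence, phenotype and arm would be 8 terms on about 30 events, fewer than 4 per term.

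The last point changes the remedy but does not rescue the screen, which does most harm in that small subset.

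**Conclusion.** The concern holds in a limited form. For predictors hypothesised in advance, the p<0.10 screen withholds adjusted estimates and tends to overstate weak effects that survive. For predictors measured in everyone, the effect is moderate at HR 1.2 per SD, small at 1.3 and negligible at 1.5. For topography it is material throughout that range: 28% to 74% of real effects are dropped, and the retained hazard ratio averages 1.49 to 1.64 for true values of 1.2 to 1.5.

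These sizes depend on about 120 and 30 events and on illustrative hazard ratios, since the documents supply neither. The direction of the problem for weak effects does not depend on the exact counts. No stated sample-size figure is disputed, and the cotinine analysis is untouched. The change is worth making because it improves the analysis of a named aim at little cost.

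**What to change.** In section 9.2, remove the screen for the hypothesised predictors and pre-specify two Cox models:

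1. **All randomised participants:** arm, expired CO, baseline dependence score and metabolism phenotype. With one term each, about 120/4 = 30 events per term.
2. **Topography subset:** the same terms plus one topography measure named in advance. About 30/5 = 6 events per term.

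Report every adjusted hazard ratio with its 95% interval whatever the p-value. Limit any p-value screening to additional covariates, labelled exploratory. State the visit at which CO and topography are taken. Section 7.2.2 allows some biomarkers to be assayed only in subgroups, so also confirm that the phenotype will be available for everyone; otherwise the event count for the first model falls.

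**Cost:** no new participants, visits or data for topography, CO or dependence; mainly SAP wording. The real downside is that one topography measure must be chosen beforehand and the subset model will be imprecise. Its intervals will be wide and should be presented as such.

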10.1. Confidentiality

The majority of study data at both sites will be collected and managed using REDCap (Research Electronic Data Capture). REDCap is a secure web application designed to support data capture for research studies, providing user-friendly web-based case report forms. REDCap is HIPAA compliant. Data are stored on a secure server at Hershey Medical Center and data in REDCap are encrypted. Access to the database requires authentication (a unique username and password) and a user matrix will be used to ensure that only appropriate data are accessed based on the individual's role on the project. Every interaction with the data is logged in REDCap creating an audit trail.

Paper files will be kept to a minimum and those that are generated will be stored in locked filing cabinets in the research offices of [name]. Electronic data stored outside of REDCap (i.e. smoking topography data) will be stored on password protected computers and password protected file share directories.

10.1.1. Identifiers associated with data and/or specimens

The following personal identifiers will be collected:

- Name
- Address
- Phone numbers
- Email addresses
- Date of birth
- Code number

1. Use of Codes, Master List

Majority of study data will be collected in REDCap including a participant record number and a study specific code number. The list connecting the participant data to the code numbers will be stored electronically in REDCap and will not be destroyed. The PIs, Study Coordinators, Research assistants and Lab Managers will have access to the list.

10.1.2. Storage of Data and/or Specimens

- **Electronic data** will be stored indefinitely in REDCap with identifiers attached. Smoking topography data will be stored electronically on password protected computers and password protected file share directories managed by Public Health Sciences (PHS) IT department.
- **Paper records:**
 - Paper will be stored with ID code number and/or participant name attached indefinitely in locked filing cabinets in the research offices of [name]. Paper records will be scanned and uploaded into participant records in REDCap. Electronic copies will be stored indefinitely as above.
- **Specimens:**
 - Prior to processing, samples will be placed in a refrigerator by the research assistant or study coordinator in the key-card secured lab of [name].
 - Within 24 hours, samples will be processed by a lab manager and will then be secured in a freezer located in the locked research laboratory of [name] on the 3rd floor of the Cancer Institute.
 - Specimens will be stored with a code number attached.
 - To manage the specimens within the freezer the lab manager will be using software called Freezerworks which will be housed on the PHS password secured file share directory on the PHS secure network. The code number, visit number, date/time of collection, processing and storage, and consent options for future use of samples will be stored here in addition to REDCap.

10.1.3. Access to Data and/or Specimens

Electronic data: PI's, Study Coordinators, Research Assistants, and lab manager will have access to the REDCap data and password protected file share directories.

However, a REDCap user matrix will limit access to data based on the researcher's role in the study.

Paper records: PI's, Study Coordinators, and Research Assistants will have access to the paper records.

Specimens: Only the study coordinators, lab manager/technicians, and PIs will have access to the specimens and Freezerworks once they have been processed and secured in the freezer room.

10.1.4. Transferring Data and/or Specimens

Processed, frozen specimens from the George Washington University study site will be shipped via commercial carrier or driven to [name] State laboratory for storage and eventual analysis. Only ID code numbers will be attached to these specimens.

10.2. Privacy

The research team will only have access to data that they have consented to provide and is provided by the participant during data collection contacts. HIPPA guidelines will be followed for all participants. Participants will be informed that they can refuse to answer any questions that make them feel uncomfortable. The majority of personal data that the participants provide

will be entered directly into REDCap by the participant. All study visits, data collection and procedures will be completed in private consult rooms at the Penn State Hershey CTSI.

11. Data and Safety Monitoring Plan

11.1. Periodic evaluation of data

The Biostatistics Core will prepare a cumulative report of all data points listed below for the Safety Monitor to review every 6 months after recruitment begins. The report will include site information.

11.2. Data that are reviewed

Data that will be reviewed include:

- Baseline sociodemographic characteristics
- Accrual and retention
- Adverse and serious adverse events
- Protocol deviations/violations
- Changes in conflicts of interest
- Patients' ability to achieve study requirements (compliance)
- Changes in cigarette consumption from baseline
- Exhaled carbon monoxide increase from baseline

Other information:

- Copy of Current IRB approved protocol
- Copy of Current IRB approved Consent Form
- Most recently submitted IRB Continuing Review

11.3. Method of collection of safety information

All safety data will be directly coded into REDCap during study visits across both sites and will be accessible at all times to the sponsor site. Every study visit participants will be asked a series of standard questions that would trigger an assessment for an adverse event to be documented. An adverse event will also be documented if a participant volunteers information about changes in their health either at study visits or on phone call interviews. An adverse event log will be used to document the description of the adverse event including, start/stop dates of event, type, grade, attribution to the study treatment, expected/unexpected, and action taken.

11.4. Frequency of data collection

Adverse events will be collected at every visit and also may be collected when the participant volunteers information between visits (e.g. phone call interviews). Carbon monoxide levels will be collected at every clinic visit. Cigarettes smoked per day will be collected at every clinic visit and during phone call interviews. Compliance will be monitored throughout the trial by a) daily diary records; b) product accountability logs where the amount of product dispensed will be recorded and unused products collected and recorded; and c) questionnaires administered and clinic visits and during phone calls regarding the use of other tobacco or nicotine products. Cumulative data will be gathered every 6 months for review by the Study Monitor.

11.5. Individual's reviewing the data

[name]., M.P.H (Professor of Medicine, Expertise: Pulmonary Medicine) will be the Study Monitor and will be responsible for reviewing the DSM report. The research coordinator will be responsible for the daily oversight of the study and recording safety data. The PI and, if needed, the Study Monitor will review all adverse events.

11.6. Frequency of review of cumulative data

Cumulative data will be reviewed every 6 months after recruitment begins. The study monitor will review the report and make appropriate recommendations to continue research as is, continue research with modification, or discontinue research in the event of significant efficacy difference between groups or unacceptable adverse events. A copy of the Study Monitor's review of the DSM report will be shared with the PI, Penn State IRB, NIH, and any other appropriate regulatory bodies.

11.7. Statistical tests

Basic descriptive statistical methods will be used to analyze the safety data to determine whether harms are occurring. Changes in cigarette consumption from the baseline will be calculated. The exhaled carbon monoxide increase from baseline will be examined in the same way. In addition, the accrual and retention-dropout rate, completion rate, and the proportions of adverse events (AE) and serious adverse events (SAE) will be generated.

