1.2. Primary Study Endpoints

1.2.1. Product compliance/drop-out

1.3. Secondary Study Endpoints

- 1.3.1. Nicotine and withdrawal symptoms- Fagerstrom Test for Nicotine Dependence, Hooked on Nicotine Checklist, Stages of Change, Minnesota Withdrawal Scale, Questionnaire on Smoking urges
- 1.3.2. Nicotine metabolites, smoke exposure biomarkers, oxidative stress biomarkers
- 1.3.3. Smoking topography (puff volume, puff count, puff duration, puff intensity)
- 1.3.4. Stress biomarkers (cortisol) and questionnaires (Kessler 6, Perceived stress, CESD)

2. Background

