4.2. Recruitment process

This will be a randomized trial of cigarette smokers (n=400 with an expected dropout rate of 30% for a total of 280 smokers) recruited at two sites: Pennsylvania State University (n=200) and George Washington University (n=200). Recruitment materials will direct cigarette smokers to contact the study center by telephone or visit the Penn State TCORS website to complete the basic eligibility screener also called the Call routing screener- IRB protocol STUDY00002213). Once they complete this screener and they are eligible for one of our studies, they will be forwarded to the appropriate study coordinator for further screening.

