21.7. Stopping Rules

No formal *a priori* statistical stopping rules will be used for interim monitoring of the primary or secondary endpoints given the risk involved in the study. Analyses will be performed and comprise of endpoints associated with safety and study integrity i.e. recruitment rate, completion rate, rates of SAEs/AEs (including changes in cigarette consumption/exhaled carbon monoxide from baseline), and any other variables that are requested from the study monitor. An unblinded bi-annual summary report of these analyses will be prepared by the Biostatistics Core for the study monitor to review. The study monitor will use these reports as the primary basis assessing data

quality and subject safety, and if necessary making recommendations of amendment to the protocol or stopping the trial.

22. Study Monitoring, Auditing and Inspecting

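### Adverse event summaries take no account of time at risk, so if drop-out differs by arm in amount or timing, the arm that loses more people can look safer than it is

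*Combined protocol and SAP*

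**What the plan says.** Section 11.7 describes the safety analysis for the six-monthly report: "Basic descriptive statistical methods will be used to analyze the safety data to determine whether harms are occurring". For adverse events the measure is a proportion, listed next to drop-out and completion rates: "the accrual and retention-dropout rate, completion rate, and the proportions of adverse events (AE) and serious adverse events (SAE) will be generated". Section 21.7 describes the report under a different term, "rates of SAEs/AEs (including changes in cigarette consumption/exhaled carbon monoxide from baseline", and adds that "An unblinded bi-annual summary report of these analyses will be prepared by the Biostatistics Core for the study monitor to review". Neither section says whether the unit is events or participants, what the denominator is, or how unequal follow-up is handled. Section 9.2 covers biomarkers, drop-out predictors and stress, but not adverse events.

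On collection, section 11.3 says: "Every study visit participants will be asked a series of standard questions that would trigger an assessment for an adverse event". Otherwise an event is documented if the participant volunteers it (sections 11.3, 11.4 and 21.2). The question lists for the seven phone surveys in section 7.2 contain no adverse event item. Under section 3.3.2, data are used up to the withdrawal date. People who withdraw are asked why they left, and no adverse event enquiry is stated.

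On drop-out, section 4.2 plans "n=400 with an expected dropout rate of 30% for a total of 280 smokers", and section 1.2 lists as primary endpoint "1.2.1. Product compliance/drop-out". Section 9.1 sizes the trial on plasma cotinine. No section gives drop-out by arm.

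**The concern.** A participant who leaves at week 6 has had a third of the 18 randomised weeks in which to have an event, and two of the six post-randomisation clinic visits at which to be asked about one. A proportion of those randomised counts that person as event-free on the same footing as someone followed to Visit 9.

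This would not matter much in a trial with little attrition. Here 30% is planned for, drop-out is part of the listed primary endpoint, and section 12 names withdrawal symptoms as a risk of the lower-nicotine cigarettes. Unequal attrition is therefore a realistic prospect, though not a stated one.

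The study monitor receives the report unblinded and, under section 11.6, may recommend stopping for unacceptable adverse events. Section 21.7 sets no formal statistical stopping rule and makes these summaries the main basis for judging safety. A modest true excess in the arm with more attrition could appear as no difference. In addition, at each six-monthly cut some participants will be part-way through. Randomisation should balance this between arms, but it means the proportion does not estimate an 18-week risk.

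**Working it through.** **The plan's own figure.** Section 9.1 needs 280 evaluable participants and allows 30% drop-out: 280 / (1 − 0.30) = 400. This reproduces. The documents state no adverse event figure to reproduce.

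**Inputs.** From the documents: 18 randomised weeks (section 7.1), 30% overall drop-out, 1:1 allocation (section 7.4.3). Assumed: the same event hazard in both arms with a true 18-week risk of 10% to 70%; constant hazards; events independent of drop-out; drop-out of 30/30, 25/35 or 20/40 per cent, each averaging 30%.

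**Formula.** With event hazard λ = −ln(1 − risk)/18 and drop-out hazard μ = −ln(1 − drop-out)/18, the expected proportion with a first event before drop-out is

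P = λ/(λ+μ) × [1 − exp(−18(λ+μ))].

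**Worked case, true risk 30% in both arms** (λ = 0.01982 per week):
- 20% drop-out, μ = 0.01240: 0.01982/0.03221 × (1 − 0.70 × 0.80) = 0.6151 × 0.44 = 27.1%.
- 40% drop-out, μ = 0.02838: 0.01982/0.04819 × (1 − 0.70 × 0.60) = 0.4112 × 0.58 = 23.8%.
- Ratio 0.88, although the true risk is identical.

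**Across assumed risks:**

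| True 18-week risk | 25% v 35% drop-out | Ratio | 20% v 40% drop-out | Ratio |
|---|---|---|---|---|
| 10% | 8.7% v 8.2% | 0.936 | 9.0% v 7.9% | 0.876 |
| 30% | 26.3% v 24.7% | 0.939 | 27.1% v 23.8% | 0.881 |
| 50% | 44.2% v 41.6% | 0.942 | 45.4% v 40.3% | 0.888 |
| 70% | 62.6% v 59.3% | 0.948 | 64.1% v 57.6% | 0.898 |

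At 30% v 30% the ratio is 1.00. If an event counts only when the participant attends the next three-weekly visit, the ratios are 0.93 to 0.94 (25/35) and 0.86 to 0.88 (20/40).

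**What could be hidden.** For true risks of 10% to 50%, and over both recording assumptions, equal observed proportions would conceal a hazard ratio of about 1.07 to 1.11 (25/35) or 1.15 to 1.23 (20/40) in the arm losing more people.

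**Timing** (true risk 30%, drop-out 20% v 40%). If all events fall in weeks 0-3, the proportions are 29.5% v 28.8%. If all fall in weeks 9-18, they are 25.5% v 20.7%, ratio 0.81.

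**Does a person-week rate repair it?** With constant hazards, yes. Person-weeks to first event or drop-out are (1 − 0.56)/0.03221 = 13.66 and (1 − 0.42)/0.04819 = 12.03 per participant. The rates are 0.2707/13.66 and 0.2385/12.03, both 1.98 per 100 person-weeks.

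With a late-rising hazard, not fully. Take 0.02 per week to week 12 and 0.08 afterwards, in both arms, with 20/40 drop-out:
- Proportions: 44.9% v 38.0%, ratio 0.85.
- First-event rates: 0.4486/13.06 = 3.43 and 0.3795/11.57 = 3.28 per 100 person-weeks, ratio 0.96.
- Kaplan-Meier cumulative incidence, with drop-out as independent censoring, targets 1 − exp(−(12 × 0.02 + 6 × 0.08)) = 51.3% in both arms.

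Cumulative incidence is therefore needed beside the person-week rate.

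**The case against.** The strongest reply is that the plan leaves the measure undefined rather than choosing a wrong one. Section 21.7 says rates, no denominator is given, and an exposure-based rate is not ruled out. That is fair as far as it goes. But section 11.7 says proportions, and nothing in either section brings in time at risk, so the same edit is needed on either reading.

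Second, the monitor is not confined to one table. Section 21.7 adds further analyses and lets the monitor request other variables, drop-out is printed alongside, and individual events are reviewed (sections 11.5 and 22.1.2). Serious events go to the FDA within five business days regardless of cause (section 20.4). A reader might infer that section 11.7 is the only safety analysis or that the monitor decides on these proportions alone. The documents do not support either inference. Even so, seeing an imbalance in drop-out does not correct the proportions.

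Third, the effect may be small. At a 10% true risk and 25/35 drop-out the gap is 8.7 − 8.2, about half a point. With 200 per arm, the 95% margin on a difference between proportions near 50% is 1.96 × √(2 × 0.25/200) = ±9.8 points, wider than any gap in the table. This stands as a limit on size. The bias would still run in one direction for a given drop-out pattern.

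Fourth, person-week rates alone leave some bias when the hazard changes over time, as shown above. That is accepted and shapes the fix.

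**Conclusion.** The point holds in conditional form: the arm that loses more people can look safer, if drop-out differs in amount or timing. With equal constant hazards the understatement is about 5-6% in relative terms at 25% v 35% drop-out and 10-12% at 20% v 40%. It is zero with equal drop-out, small if events cluster early and larger if they cluster late. It also disappears if the extra drop-outs leave only after their event has been recorded.

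A reader might infer that the reduced-nicotine arm will in fact look safer than it is. The documents do not support that. They give 30% overall, no figure by arm, no adverse event risk and no event timing, so every by-arm figure here is an assumption. Nor does the point depend on drop-out being the sole endpoint, since the trial is sized on cotinine. The change is worth making because attrition is expected to be substantial and a better summary is available from dates already collected.

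**What to change.** In sections 11.7 and 21.7, use one defined measure in place of the two terms, stating whether it counts events or participants and over which denominator. Beside the proportions, report by arm:

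- adverse events and serious adverse events per person-week, from randomisation to last contact or Visit 9, whichever is earlier;
- cumulative incidence of first adverse event and first serious adverse event, by Kaplan-Meier with censoring at last contact. If a competing-risk estimator is used, drop-out should still be censored, because treating it as a competing event leads back to the crude proportion;
- time to drop-out, in the same report.

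Report Treatment Choice Phase events separately. Participants then choose their own path, and those who try to quit have extra contacts at which events are assessed.

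The cost is a few table columns. Event start and stop dates are in the adverse event log (section 11.3), and time from randomisation to drop-out is already needed for the Cox analysis in section 9.2. The report should state two limits: these measures assume that leaving is unrelated to unrecorded events, and they cannot recover events that cause withdrawal and are never reported.
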